5. Subjects with a history of an eating disorder requiring medical or behavioral treatment within the past 10 years.
6. Subjects with prior small bowel or colonic surgery (excluding appendectomy or cholecystectomy if over 6 months since these 2 procedures)
7. Oral antibiotic use in the past 3 months
8. Any planned significant changes in dietary or exercise regimen within 30 days prior to Screening or during the study.
9. Currently pregnant or breastfeeding.

Concomitant Medications

[figure not shown]
Subjects will be allowed to remain on their current IBS medications, provided a stable dose in the past 30 days and they fulfill entry criteria for symptom frequency and severity.

Study Design

This pilot study is designed to assess the comparative effectiveness of MD with LFD. Approximately 20 subjects will undergo a seven-day baseline screening period during which symptoms will be recorded. If a subject doesn't meet all eligibility criteria in the first seven days of the baseline screening period, the screening period can be extended up to 21 days. Subjects meeting all eligibility criteria will be randomized in a 1:1 ratio to receive either the MD or the LFD for a four-week period.

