Diet interventions and delivery: Patients randomized into the LFD cohort will receive meals and snacks that are low in all FODMAP groups (lactose, fructose, polyols, etc.). The diet for the LFD cohort is essentially a re-creation of the clinically used restriction phase of the low-FODMAP diet. Patients randomized into the MD will receive meals and snacks that are consistent with an MD (plant-based foods, olive oil, etc.). We and others have shown that among the FODMAPs, fructans are the most likely culprit for IBS patients.^{37,39} To ensure the MD group was not receiving very high amounts of fructans, we decided to limit the fructan content in the MD group to 4 grams/day, the average daily fructan consumption in the general US population.⁴⁰ This will ensure MD diet these patients are receiving is not low in fructan but is not very high either and is close to the US general population. Meal Delivery: Three meals and 2 snacks per day (approximate 2000 kcal/day) will be shipped several times per week by ModifyHealth. ModifyHealth has agreed to provide us with all the meals for every patient for the entire study duration without any cost (beyond this they will not have any role in data collection, analysis, and interpretation). Subjects will be instructed not to eat outside of the food provided and extra food shipment for emergency use will be provided at the beginning of the study. Meals for both groups will be packaged identically.

Blinding: To best ensure the validity of the data collected, as well as the ability to evaluate the efficacy of the MD, participants will be blinded to the mechanics and specifics of the diets provided. Participants will know that both diets (the Mediterranean and low FODMAP) may help improve their IBS symptoms but will not know that these specific diets are being compared. Instead, participants will be told that the study is investigating two different diets for IBS, and they will be receiving either Diet A or Diet B, differing in the types and amounts of specific foods provided. Furthermore, study coordinators and investigators from the site will be blinded to which diet the participant receives.

Screening Visit (Visit #1)

- Informed consent will be obtained from the subjects.
- Medical history including IBS history will be obtained from the subjects.
- Blood samples will be obtained.
- Vitals, weight and height will be obtained

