- Pregnancy test will be obtained in women of childbearing age if no reliable method of contraception is being utilized (e.g. IUD, OCP, implant)
- Subjects will be given two stool collection kits for at-home collection. One stool sample will be collected prior to beginning the treatment period. One stool sample will be collected on Day 28 (-1 day).
- Subjects will be instructed on the online questionnaires according to Chart A (described below) which will assess periodic symptoms and diet compliance to be completed for the duration of the study.

- Subjects will be instructed on the 3-day food diary to assess for nutritional content to be completed at the start and end of the study.
- A detailed dietary history will be obtained.

Screening Period

- Subjects will complete a 3-day food diary which will be analyzed for nutritional content.
- Subjects will complete a daily online questionnaire to assess symptoms
- For subjects who don't meet all eligibility criteria in the first seven days of the screening period, this period can be extended up to 21 days

Day 0 Visit (Visit #2)

- Patients who fulfill the inclusion and exclusion will be randomized to either the Mediterranean or low FODMAP cohorts (Diets A and B)
- Vitals will be obtained including height and weight at visit 2

Treatment Period

- Subjects will fill out a daily online questionnaire to assess symptoms and diet compliance according to Chart A throughout the treatment period.

Day 28 (End-of-treatment) Visit

- Subjects will complete a 3-day food diary which will be analyzed for nutritional content and compliance
- Adverse events and concomitant medications will be reviewed.
- Blood samples will be obtained.
- Post-treatment stool samples will be collected.
- Subjects will finish the last set of questionnaires

Clinical Outcome Measures

Online questionnaire entries will include the following measures, to be assessed on a frequency according to Chart A.

- Abdominal Pain Intensity: The abdominal pain score is a single-question, 11-point numeric rating scale in which 0 represents no abdominal pain and 10 represents the worst possible abdominal pain. Once per day, subjects will report their worst daily (in the past 24 hours) abdominal pain.

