- Abdominal pain intensity – Proportion of patients who would be weekly responders to abdominal pain for at least 2 of the 4 weeks. A weekly responder is defined as a decrease in the weekly average of worst abdominal pain in the past 24 hours score of at least 30% compared with baseline.

Secondary Endpoints

- Adequate relief - Proportion of patients who would be weekly responders to adequate relief symptom assessment for at least 2 of the 4 weeks. A weekly responder is defined as adequate relief in symptoms in at least 2 out of 4 weeks of the treatment period.
- IBS-SSS - Proportion of weekly responders for at least 2 of the 4 weeks. A weekly responder is defined as a decrease in the weekly IBS-SSS score of at least 50 points compared with baseline.
- Bloating - Proportion of patients who would be weekly responders to bloating for at least 2 of the 4 weeks. A weekly responder is defined as a decrease in the weekly average of worst bloating in the past 24 hours score of at least 30% compared with baseline.
- Stool consistency: Proportion of patients who would be weekly responders to stool consistency assessment for at least 2 of the 4 weeks. A stool consistency weekly responder will be defined as a 50% or greater reduction in the number of days per week with at least one abnormal stool (defined as BSS 1 or 2 or 6 or 7)

Exploratory endpoints:

- Mean changes in stool frequency, abdominal discomfort, IBS-QoL, anxiety, fatigue, brain fog, and sleep quality will be measured before and after the study.
- Stool and sera will be collected during the study and stored for future analyses. The stool will be stored for microbiome analysis, fermentation indices (short-chain and branched-chain fatty acid profiles), and bile acid profile and serum will be stored for analysis of the effect of diets on permeability using serological markers such as LPS, LBP, Zonulin, and inflammatory cytokines.
- Changes in breath hydrogen and methane pattern with the dietary interventions

Statistical Analysis

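### The only pre-diet blood sample is drawn at screening, so the exploratory within-arm serum change spans about 35 to 49 days for a 28-day diet

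*Combined protocol and SAP*

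**What the plan says.** - **Blood draws.** The Screening Visit (Visit #1) lists "Blood samples will be obtained", and the Day 28 (End-of-treatment) Visit repeats the item. No other visit lists blood.
- **Day 0 Visit (Visit #2).** The entries are randomisation and "Vitals will be obtained including height and weight at visit 2".
- **Timing.** Study Design sets a seven-day baseline screening period and adds that "the screening period can be extended up to 21 days" for those who do not qualify at once. Eligible patients are then "randomized in a 1:1 ratio to receive either the MD or the LFD for a four-week period".
- **Use of the serum.** Under Exploratory endpoints, "serum will be stored for analysis of the effect of diets on permeability using serological markers such as LPS, LBP, Zonulin, and inflammatory cytokines". The samples are to be kept for later analysis.
- **Analysis.** Statistical Analysis gives one approach for continuous data: a paired t-test or a Wilcoxon signed-rank test, before versus after the diet. It names no between-arm test for a continuous change.
- **Conditions of the draw.** Neither visit states a fasting, meal or time-of-day condition. The other biomarkers have an anchor: the second stool sample is tied to Day 28 with a one-day window, and breath gas is read before the first and last meal of the day.

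**The concern.** The serum is meant to show what the diets do to permeability and inflammatory markers. The natural baseline is the last moment before the first study meal. The plan takes it at the consent visit instead, before the symptom diary begins, and then leaves a gap that differs from patient to patient. The inclusion and exclusion criteria need no blood result; the pregnancy test is a separate item with no specimen stated. Nothing in the documents explains the early draw.

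What is at stake is the reading of the paired serum change, the only analysis named for such data. It would attribute to 28 days of diet whatever moved over a longer period that includes weeks on the habitual diet. Plans for future funding for the future project relies on these biospecimens to support a larger application with mechanistic aims, and a stored sample cannot be re-timed.

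**Working it through.** **1. Interval between draws.** Inputs: screening of 7 days, or up to 21 (Study Design; Screening Period), and a diet of four weeks, or 28 days (Study Design). I assume that Visit 1 opens the screening period and that the diet starts at Day 0. The documents fix neither, so the gap could be longer.

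- Shortest: 7 + 28 = 35 days; off-diet share 7/35 = 20%.
- Longest: 21 + 28 = 49 days; off-diet share 21/49 = 43%.

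**2. Within-arm change.** The documents give no drift, SD or pre/post correlation (ρ), so these are assumptions, in SD units. With no diet effect and a drift of −0.3 between draws, simulation (20,000 replicates, 10 per arm) gives a mean change of about −0.30 in each arm. The SE of a within-arm mean change is √(2(1−ρ)/10): 0.32 at ρ = 0.5 and 0.14 at ρ = 0.9. Such a drift is about one to two SEs.

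If the drift accrued evenly, a Day 0 draw would remove only the screening part: 0.3 × 0.20 = 0.06 to 0.3 × 0.43 = 0.13. The rest would remain.

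**3. Between-arm difference in change.** In the same simulation this averages 0.00. Drift common to both arms cancels.

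Unequal gaps add some variance. Suppose the whole −0.3 arose in a 21-day screening at a constant rate, hence −0.1 in a 7-day one. The largest possible SD of drift across patients is half that range, 0.1, which adds 0.01 to the per-patient variance of change, 2(1−ρ). The between-arm SE, √(2 × variance/10), moves from 0.447 to √(2 × 1.01/10) = 0.449 at ρ = 0.5, and from 0.200 to √(2 × 0.21/10) = 0.205 at ρ = 0.9.

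The larger route is a lower correlation over a longer interval: √(4(1−ρ)/10) is 0.20 at ρ = 0.9 and 0.53 at ρ = 0.3. The documents do not say how far ρ would fall.

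**4. Uncontrolled meals.** Assume, only for illustration, independent meal-related noise of SD 0.5 at each draw, alike in both arms. The variance of change becomes 2(1−ρ) + 0.5.

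| ρ | SE without noise | SE with noise | Variance ratio |
|---|---|---|---|
| 0.5 | 0.45 | 0.55 | 1.5 |
| 0.7 | 0.35 | 0.47 | 1.8 |
| 0.9 | 0.20 | 0.37 | 3.5 |

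Simulation agrees to within 0.01 and shows no between-arm bias. Because it gave both arms the same noise, it does not test an arm-specific meal response.

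**The case against.** The case against is substantial. The endpoint is exploratory, the samples are stored, and the pilot has about 20 patients. The interval is calendar arithmetic, not a measured error, and 21 days applies only to extended screenings. The protocol also limits drift: it excludes planned significant diet or exercise changes from 30 days before screening and oral antibiotics in the past 3 months, and it requires stable doses of IBS medication for 30 days. Silence on fasting in a short protocol does not show that draws will be unfasted. All of this stands, and it sets the priority. It does not supply a reason to draw before Day 0.

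A reader might infer three stronger things.

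- **That the early draw biases the comparison of diets.** It does not. The draw precedes randomisation and the schedule is common to both arms.
- **That the last study meal before Day 28 creates a between-arm bias which randomisation cannot remove.** Such a distortion would equal the fraction of patients fed times the arm difference in acute response. The documents give neither. They do not say that these markers respond to meals, and they give no fat content for the low-FODMAP meals. An effect of assigned meals is also arguably part of the assigned diet's effect. What remains is conditional: if there is an acute response, unfasted samples cannot separate it from a sustained change.
- **That the serum necessarily predates the pre-diet stool by the same gap.** Stool may be collected at any time before treatment, including soon after Visit 1.

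**Conclusion.** The point holds as a low-priority scheduling weakness. The only listed pre-diet blood sample is taken about 7 to 21 days before Day 0, so the paired serum change covers about 35 to 49 days for a 28-day diet. The within-arm change absorbs off-diet drift that varies by patient, and an arm comparison loses some precision. The randomised comparison is not biased by the timing. The missing fasting and time-of-day condition matters to the extent that the markers respond to recent meals, which is an assumption here.

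The interval rests on Visit 1 starting the screening period and the diet starting at Day 0; every figure in SD units rests on assumed values. The primary and secondary endpoints are unaffected. Nor should a reader infer that a Day 0 draw would isolate the diet effect: a within-arm change over 28 days still contains time and expectation effects and regression to the mean.

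**What to change.** - Move the pre-diet draw from Visit 1 to the existing Day 0 visit, before the first study meal.
- Take the Day 0 and Day 28 samples under the same fasting and time-of-day condition. At the least, record clock time and time since the last meal at each.
- Take the Day 28 sample while the patient is still on study meals, for example within the one-day window already used for stool.

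The cost is a schedule amendment and two overnight fasts; recording meal times instead would avoid the fasts. No visit or draw is added, and patients who fail screening are spared a blood draw. Separately, when the serum analysis is specified, a baseline-adjusted comparison of the arms would answer the diet question more directly than the paired change.

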All continuous variables will be tested for normality using the Shapiro-Wilk test. Normally distributed continuous data will be presented as mean (+/- SD) and will be compared pre-and post-dietary interventions using paired Student's t-test. Continuous data which are not normally distributed will be presented as median (range) and compared using Wilcoxon signed-rank test. Proportions will be expressed as percentages and compared using a chi-square test or fisher exact test as appropriate. As this is a pilot feasibility study, a sample size of 20 patients will allow us to get data on the outcomes and non-inferiority margin needed to power the larger Phase III multi-centered trial.

Potential difficulties

One of the potential difficulties might be the difficulty in patient recruitment for the study. Our group has successfully completed several pharmacological and diet-based RCTs in this patient population and has been able to recruit a much larger sample size for previous studies. However, to ensure we can recruit the required sample size, we will assign a study coordinator who will dedicate a significant proportion of her/his time to

recruiting patients from our functional and general GI clinics. Online and on-site advertisements will also be utilized to recruit patients from general gastroenterology and primary care clinics. We will further utilize a novel digital recruiting tool called “My GI Health” which will identify potential study subjects through social media platforms. We feel that this study will be attractive as we will be providing meals for the duration of the study. In addition, the lack of a placebo group will ensure that all participants will receive a potentially beneficial diet intervention. Other potential difficulties include patients being non-compliant with the diet. We are providing meals to all participants to minimize this and will obtain a daily food log, 3-day recall as well as MEDAS (Mediterranean Diet Adherence Scale) to ensure that our patients are compliant with their allocated diet arm.

Limitations

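### Pain, bloating and IBS-SSS are compared between diets only as yes/no responder status; a between-arm, baseline-adjusted analysis of the scores should be pre-specified alongside.

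*Combined protocol and SAP*

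**What the plan says.** **Data collected.** Under Clinical Outcome Measures, pain is a 0-10 score: "Once per day, subjects will report their worst daily (in the past 24 hours) abdominal pain". Bloating is scored daily in the same way, and IBS-SSS is completed at the start and weekly (Chart A).

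**Endpoints.** The primary endpoint is "Proportion of patients who would be weekly responders to abdominal pain for at least 2 of the 4 weeks", where a weekly responder has "a decrease in the weekly average of worst abdominal pain in the past 24 hours score of at least 30% compared with baseline". The bloating endpoint is "Proportion of patients who would be weekly responders to bloating for at least 2 of the 4 weeks", again with a 30% cut. IBS-SSS uses a 50-point cut in at least 2 of 4 weeks. Mean change appears only under Exploratory endpoints: "Mean changes in stool frequency, abdominal discomfort, IBS-QoL, anxiety, fatigue, brain fog, and sleep quality will be measured before and after the study". Pain, bloating and IBS-SSS are not in that list.

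**Tests.** For continuous variables the Statistical Analysis section names a paired t-test or a signed-rank test, before against after diet. For proportions: "Proportions will be expressed as percentages and compared using a chi-square test or fisher exact test as appropriate". No covariate adjustment is mentioned.

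**Size and purpose.** Patients are "randomized in a 1:1 ratio to receive either the MD or the LFD for a four-week period", and "a sample size of 20 patients will allow us to get data on the outcomes and non-inferiority margin". Both aims under Specific aims are comparisons of MD with LFD. No alpha, power, effect size or SD is given.

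**The concern.** The aims concern the difference between diets, yet the only named method that can compare the arms works on proportions. Up to 28 daily treatment scores, plus a screening week, are reduced to one yes/no per patient before the arms are compared. A patient who improves by 29% counts the same as one who worsens, and one who improves by 31% the same as one who becomes pain-free. The paired tests, applied within an arm or to all patients together, do not estimate a difference between diets.

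Two things are at stake. First, the protocol foresees that MD might prove inferior, but the planned comparison has little chance of showing even a large shortfall. Second, the pilot is meant to inform a larger non-inferiority trial, and a between-arm difference in score with its residual SD is among the most useful things it could deliver. The plan does not commit to producing either.

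**Working it through.** **1. Plan's own figure.** The total of 20 is justified as a pilot size with no design inputs, so there is nothing to reproduce.

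**2. Inputs.** From the documents: 20 patients, 1:1, hence about 10 per arm; LFD improves symptoms in 50-60% (Specific aims; a figure for general symptom improvement, used here as a proxy for the pain responder rate). Assumed: two-sided alpha 0.05, MD responder rate 20-40%, no dropout.

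**3. Which test applies.** With 10 per arm and R responders in total, the expected counts are R/2 and (20 - R)/2 in each arm. Under the usual rule that chi-square needs every expected count to be at least 5, this happens only at R = 10. In those tables chi-square and Fisher reach the same decision, so in practice the planned test has Fisher's power.

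**4. What Fisher needs.** If LFD has 6/10 responders, MD must have 0/10 (p = 0.011); 6 v 1 gives p = 0.057. With 6/10 in both arms, the 95% Newcombe interval for the difference is -37 to +37 percentage points.

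**5. Power on the two scales.** Fisher and uncorrected chi-square by exact enumeration of all 10 v 10 tables. The t-test uses the noncentral t with 18 df and noncentrality d × √(10/2), where d = z(p_LFD) - z(p_MD), assuming a normal score with equal variances. For 60% v 30%, d = 0.253 + 0.524 = 0.78.

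| LFD v MD | d | Fisher | Chi-square | t-test on score |
|---|---|---|---|---|
| 60% v 40% | 0.51 | 5% | 13% | 19% |
| 60% v 30% | 0.78 | 12% | 25% | 38% |
| 60% v 20% | 1.09 | 25% | 42% | 64% |
| 50% v 20% | 0.84 | 13% | 25% | 43% |

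**6. Splitting the gap.** At 60% v 30% the gap is 38 - 12 = 26 points. Moving from Fisher to chi-square recovers 25 - 12 = 13 of them, about half. The true type I error at a common 50% rate is 1.3% for Fisher and 4.2% for chi-square.

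**7. Cost of dichotomising alone.** Asymptotic efficiency is φ(z)²/[p(1 - p)]: 0.64 at p = 0.5 and 0.62 at p = 0.6. Sample-size ratios for 80% power agree: 26/42 = 0.62 per arm for 60% v 30%, and 23/39 = 0.59 for 50% v 20%. The loss is therefore about 36-41%.

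**8. Simulation of the actual responder rule.** Assumed, and not in the documents: baseline mean 5.5, between-patient SD 1.4, week SD 0.9, day SD 1.5, LFD improvement 2.0 points reached at 60/90/100/100% over weeks 1-4, no missing data. MD is set 1.5 points worse. ANCOVA is of the 4-week mean on arm plus baseline.

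| SD of improvement | Fisher | ANCOVA | ANCOVA 95% CI half-width |
|---|---|---|---|
| 1.3 | about 15% | about 42% | about 1.4 points |
| 2.0 | about 8% | about 28% | about 1.8 points |

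With SD 1.3 the responder rates are 62% v 29%. With no true difference, type I error is about 5% for ANCOVA and 1.3% for Fisher.

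**The case against.** The strongest reply is that this is a declared pilot. It claims no power, admits its small size under Limitations, and uses a responder endpoint already defined relative to each patient's baseline. That stands as a reason to keep the responder endpoint primary. It does not explain why the scores have no between-arm analysis at all, since a pilot's main products are estimates and variances.

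Four stronger readings are tempting, and the documents do not support them.

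- A reader might infer that collapsing pain to yes/no by itself throws away most of the trial's ability to see a shortfall. The power loss exceeds half only for Fisher at 10 per arm, and about half of it is Fisher's conservatism.
- A reader might infer that every patient supplies at least 7 baseline and 28 treatment scores. Inclusion criterion 4 accepts 80% of entries in the screening week, and no minimum is set for treatment days.
- A reader might infer that no SD of pain change could emerge. The Statistical Analysis section speaks of all continuous variables, which could take in pain and give a paired SD of change. What is missing is a named commitment, a between-arm estimate and a baseline-adjusted residual SD.
- A reader might infer that the added analysis would make a null result informative. It would not. Even with SD 1.3, the half-width of 1.4 points is 1.4/2.0 = 70% of the assumed LFD benefit, and 80% power with 10 per arm needs d of about 1.32.

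**Conclusion.** The point holds as an omission that is cheap to repair. Followed as written, the plan makes no between-arm comparison of pain, bloating or IBS-SSS as scores and adjusts nothing for baseline, although its aims are between-diet. That rests on the text alone and is firm.

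The size is less certain. For 60% v 30% responders the power is about 12% against 38%, which depends on the assumed rates, a two-sided 0.05 test, a normal score and complete data. The simulated 15% v 42% falls to 8% v 28% when the SD of improvement rises from 1.3 to 2.0, and the documents give no SD by which to choose. In every setting shown the score analysis does better, and in most of them it is still underpowered. The risk that a null result is read as support for the hypothesis of similar improvement comes mainly from N=20 with no margin set, and no change of scale removes it.

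**What to change.** Keep the responder endpoint as primary. Add to the Endpoints and Statistical Analysis sections, before any comparison by arm:

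1. A supportive analysis of the between-arm difference in mean worst daily pain over weeks 1-4, by ANCOVA with baseline pain as covariate, or by a repeated-measures model of the weekly means. Report the estimate, its 95% CI and the residual SD for planning the larger trial.
2. The same analysis for bloating and for IBS-SSS.
3. A sentence stating that these analyses remain underpowered at N=20, and that a non-significant difference on either scale is not evidence that the diets are similar.

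The cost is plan wording and one model per endpoint. The data are already being collected, and neither the sample size nor the visit schedule changes.
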